### **3.7 Sample size determination**

#### **3.7.1 Planned Number of Subjects**

Total of 93 subjects (41 subjects with squamous NSCLC and 52 subjects with non-squamous NSCLC)

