##### **2) Data Handling**

An adverse event is any unfavorable or unintended sign (including an abnormal laboratory finding), symptom or disease during a clinical trial, whether or not related to the investigational product. Of note, tabulation will include adverse events whose symptoms have occurred/worsened during the period from the first dose of the study drug until 28 days after the final dose (or until the start of subsequent anti-cancer therapy for non-small-cell lung cancer after the final dose, whichever comes first after the final dose). In addition, all adverse events that occur during the treatment period or the subsequent anti-cancer therapy follow-up period will be listed and reported.

All adverse events reported in this clinical study will be coded by SOC (System Organ Class) and PT (Preferred Term) using MedDRA (Current version). Treatment-emergent adverse events are those events that occur or worsen on or after the first dose of study treatment up until end of study treatment.

For the analysis of adverse events, only treatment-emergent adverse events (TEAEs) will be included in the summary tables.

In case the same adverse events in terms of SOC and PT occurs to one subject more than once, it will be considered as a single event, and the highest severity and relationship status among all events will be taken into account.

Severity of adverse events will be classified using NCI-CTCAE, and where NCI-CTCAE is inapplicable, it will be classified as grade 1 ('Mild'), grade 2 ('Moderate'), grade 3 ('Severe'), grade 4 ('Life threatening or disabling/incapacitating') or grade 5 ('Death related to adverse event') based on the maximum intensity. With respect to the relationship to study drug, 'Related' will be regarded as

related, and ‘Not related’ will be regarded as unrelated. If the relationship is unclear due to a missing, the relationship to study drug is considered as ‘Related’.

(1) Time to a Grade 3 or higher adverse event will be calculated using the following formula.

- Time to a Grade 3 or higher adverse event (days) = (date of the onset of the Grade 3 or higher adverse event, or the date of worsening to Grade 3 or higher, whichever comes first) - (the first dose date of investigational product) + 1

Data will be censored if the subject has no Grade 3 or higher adverse event at 28 days after the final dose (or at the start of subsequent anti-cancer therapy for non-small-cell lung cancer after the final dose, whichever comes first).

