
(2) Time to a Grade 3 or higher adverse drug reaction will be also calculated in the same manner.

(3) Select adverse events will be defined as adverse events to be coded as PTs in any of the categories specified in [Addendum 1 List of Select Adverse Events](#) (i.e., Endocrine Adverse Events, Hypersensitivity/Infusion Reactions, Gastrointestinal Adverse Events, Hepatic Adverse Events, Pulmonary Adverse Events, Renal Adverse Events and Skin Adverse Events).

Time to a select adverse event will be calculated by category using the following formula.

- Time to select adverse event (days) = (date of the onset of the earliest select adverse event in the category) – (the first dose date of investigational product) + 1

Data will be censored if the subject has no select adverse event in any of the categories at 28 days after the final dose (or at the start of subsequent anti-cancer therapy for non-small-cell lung cancer after the final dose, whichever comes first).

(4) Time to select adverse drug reaction will be also calculated in the same manner.

(5) Number of deaths

The number of deaths will be defined as the total number of subjects who have died during the period from the first dose of the study drug until 28 days after the final dose (or until the start of subsequent anti-cancer therapy for non-small-cell lung cancer after the final dose, whichever comes first).

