### **10.1.3 Analysis Methods**

1) Overall Adverse Events, Adverse Drug Reactions and Number of Deaths

(1) The analysis results will be summarized by squamous NSCLC and non-squamous NSCLC separately and totality.

- (2) The number of subjects (incidence rate) of the overall incidence will be provided for all adverse events and adverse drug reactions). The data will be displayed as “subject number (incidence of subjects (%))”.
- (3) The numbers of deaths, subjects with Grade 3 or higher adverse events and adverse drug reactions, and serious adverse events and adverse drug reactions, and discontinuations due to adverse events and adverse drug reactions, and adverse events and adverse drug reactions led to death will be summarized.

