## 2) Classification of Adverse Events

- (1) The analysis results will be summarized by squamous NSCLC and non-squamous NSCLC separately and totality.
- (2) Adverse events and adverse drug reactions will be summarized by SOC, PT and CTCAE grade (grade 1, 2, 3, 4, and 5). The data will be displayed as “subject number (incidence of subjects (%))”.
- (3) Incidences of adverse events and adverse drug reactions by SOC and PT will be summarized. In addition, incidences of adverse events and adverse drug reactions will be summarized by SOC, PT and CTCAE grade (any grade, grade 3 or 4, grade 5). And adverse events and adverse drug reactions with an incidence at or above a certain level will be summarized by SOC, PT and CTCAE grade (any grade, grade 3 or 4, grade 5).
- (4) Incidences of adverse events and adverse drug reactions leading to death will be summarized by SOC and PT.
- (5) Incidences of adverse events and adverse drug reactions leading to discontinuation of the study treatment will be summarized by SOC, PT and CTCAE grade (any grade, grade 3 or 4, grade 5).
- (6) Incidences of adverse events and adverse drug reactions leading to interruption of the investigational product will be summarized by SOC, PT and CTCAE grade (any grade, grade 3 or 4, grade 5).
- (7) Incidences of serious adverse events and adverse drug reactions will be summarized by SOC, PT and CTCAE grade (any grade, grade 3 or 4, grade 5).
- (8) Incidences of select adverse events and adverse drug reactions will be summarized by categories, PT and CTCAE grade (any grade, grade 3 or 4, grade 5).
- (9) Incidences of select adverse events and adverse drug reactions leading to discontinuation will be summarized by categories, PT and CTCAE grade (any grade, grade 3 or 4, grade 5).
- (10) Incidences of serious select adverse events will be summarized by categories, PT and CTCAE grade (any grade, grade 3 or 4, grade 5).

(11) Kaplan-Meier curves will be presented for time to onset of select adverse events and adverse drug reactions. Kaplan-Meier curves will also be displayed for time to onset of Grade 3 or higher adverse events and adverse drug reactions.

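### The rule for merging repeated adverse events takes the highest grade and the relationship over all episodes, so the grade of an adverse drug reaction can come from an episode judged unrelated

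*SAP*

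**What the plan says.** The merging rule is in SAP 10.1.2, item 2) Data Handling. Repeats of one term in a subject are counted once; the sentence begins "In case the same adverse events in terms of SOC and PT occurs to one subject more than once, it will be considered as a". Its second half sets the attributes of the merged record: "the highest severity and relationship status among all events will be taken into account".

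The same item makes relationship a two-level variable: an event marked as related counts as "related, and ‘Not related’ will be regarded as unrelated". It also handles missing causality: "If the relationship is unclear due to a missing, the relationship to study drug is considered as ‘Related".

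The outputs that use an ADR grade are in SAP 10.1.3. The overview, item 1)(3), counts "subjects with Grade 3 or higher adverse events and adverse drug reactions". The classification tables begin at item 2)(2): "Adverse events and adverse drug reactions will be summarized by SOC, PT and CTCAE grade (grade 1, 2, 3, 4, and 5"). Items 2)(3) and 2)(5) to (9) repeat the split of ADRs by grade band, overall and for discontinuations, interruptions, serious events and select events.

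Separately, SAP 10.1.2 2)(1) defines time to a Grade 3 or higher adverse event from the date the event began at, or worsened to, that grade. Item (2) adds: "Time to a Grade 3 or higher adverse drug reaction will be also calculated in the same manner".

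**The concern.** An ADR table by grade is read as the severity of events attributed to the drug. That reading holds only if the grade and the attribution describe the same episode. The SAP's sentence applies one phrase, covering all of the subject's events under the term, to both attributes. Nothing in SAP 10.1.2 or 10.1.3 links them to one episode or says how the grade of an ADR is derived. A mild related episode can then lend its attribution to a severe unrelated one.

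The missing-causality rule widens the route. A single mild episode with no recorded causality is enough to turn a separate Grade 3 episode of the same term, explicitly judged unrelated, into a Grade 3 ADR. The same logic reaches the Grade 5 column, where a related Grade 1 episode and a later unrelated fatal episode of the same term would merge into a Grade 5 ADR.

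Two things are at stake: the Grade 3 or higher ADR rate, which is a prominent safety figure in an uncontrolled study, and its agreement with the Kaplan-Meier curve for time to Grade 3 or higher ADR (SAP 10.1.3 2)(11)).

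**Working it through.** The documents give no figure for this rule, so there is nothing to reproduce. The check compares two derivations of ADR grade for one subject and one SOC/PT.

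- **Rule A (SAP 10.1.2, plain reading):** grade = maximum over all episodes; relationship = maximum over all episodes; the merged event is an ADR if that relationship is related.
- **Rule B (related episodes first):** drop unrelated episodes, then grade = maximum over those left; no ADR if none are left.

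**The example.** Episode 1 is Grade 3, not related. Episode 2 is Grade 1, related or with causality missing.

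| Output | Rule A | Rule B |
|---|---|---|
| All-cause grade | max(3, 1) = 3 | 3 |
| ADR of any grade | yes | yes |
| ADR grade | max(3, 1) = 3 | 1 |

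Only the ADR grade changes. Any-grade ADR incidence agrees in general, because each rule finds an ADR exactly when at least one episode is related.

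**All two-episode cases.** Five grades and two relationship levels give 10 possible episodes, hence 10 × 10 = 100 ordered pairs.

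- The rules differ only when one episode is related, the other is not, and the unrelated one has the higher grade. There are 10 such grade pairs (5 × 4 / 2) in 2 orders, so 20 of 100.
- Rule A creates a Grade 3 or higher ADR with no related episode at Grade 3 or above when the unrelated grade is 3, 4 or 5 and the related grade is 1 or 2: 3 × 2 × 2 orders = 12 of the 20.
- In the other 8 the grade changes without crossing Grade 3 (for example 1 to 2, or 3 to 4).

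These are counts of logical possibilities, not expected frequencies.

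**Weight of one subject.** SAP 3.7.1 gives the planned size: "Total of 93 subjects (41 subjects with squamous NSCLC and 52 subjects with non-squamous NSCLC"). SAP 14.4 gives 96 treated subjects at the data review of 27 February 2015, without a split by histology.

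| Denominator | One subject |
|---|---|
| 93 planned, overall | 1/93 = 1.1 points |
| 96 treated at data review, overall | 1/96 = 1.0 points |
| 41 planned, squamous | 1/41 = 2.4 points |
| 52 planned, non-squamous | 1/52 = 1.9 points |

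For the overview count of subjects with any Grade 3 or higher ADR, each figure is a ceiling. The merging works per term but the overview counts subjects. A subject with a genuine related Grade 3 or higher event under another term adds nothing, and neither does one whose merged grade does not cross Grade 3.

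**Against the time-to-event analysis.** In the example, Rule A puts the subject in the Grade 3 ADR row. The time-to-event definition asks when a related event began at, or worsened to, Grade 3, and no such date exists. The subject is then either censored, so that table and curve disagree, or dated from the unrelated episode. The SAP does not say which. Under Rule B the question does not arise.

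**The case against.** The strongest reply is that the SAP never says the two attributes are taken separately. SAP 10.1.3 lists adverse events and ADRs as distinct outputs, and a programmer could restrict to related episodes before merging without contradicting any sentence. That is fair: independence of the two maxima is an inference from the wording. It is still the plain reading, since one phrase about all events governs both attributes and no section prescribes the restriction. Even on the kinder view the order of operations is unspecified, and two competent programmers could report different Grade 3 or higher ADR counts.

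A second reply is that the rule errs on the safe side. It cannot hide toxicity, it fits the decision to treat missing causality as related, all events are also to be listed, and SAP 12.2 plans no tests, so no decision rule depends on the rate. All of this stands and keeps the point minor. It does not make the tabulated grade correct: caution about causality is already supplied by the missing-data rule, and pairing attributes from different episodes describes a reaction that was not observed.

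A third reply concerns size. A reader might infer that the Grade 3 or higher ADR rates are overstated, or that every affected subject adds a full 1/n to them. The documents support neither. The situation needs repeated episodes of one term in one subject, mixed causality, and the higher grade on an unrelated episode. No frequency is given, and 1/n is only an upper limit per subject for the overall rate.

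**Conclusion.** The point holds as a minor defect in a derivation rule. As written, SAP 10.1.2 can assign an ADR the grade of an unrelated episode, so ADR-by-grade tables and Grade 3 or higher ADR counts can be overstated and can disagree with time to Grade 3 or higher ADR. All-cause grades and any-grade ADR incidence are not affected.

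The effect is at most 1.1 points overall per such subject (1.0 with the 96 treated), 2.4 in squamous and 1.9 in non-squamous. The histology figures assume the planned cohort sizes, because the split of the 96 is not given. The total effect cannot be estimated from the documents and may be zero. The conclusion rests on the plain reading of the merging sentence; if related episodes were in fact selected first, what remains is that the SAP does not say so.

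**What to change.** Replace the single merging rule in SAP 10.1.2 2) with one rule per type of table:

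- **Adverse event tables:** for each subject and SOC/PT, take the highest grade over all episodes.
- **ADR tables:** first keep only related episodes, including those with missing causality set to related; then take the highest grade among them.

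Apply the second rule to every ADR output by grade in SAP 10.1.3, and derive time to Grade 3 or higher ADR from the same set of related episodes so that table and curve agree.

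The cost is a sentence or so of text and one program filter, with no new data. The downside is that the ADR tables lose a conservative over-count, so their Grade 3 or higher rates may fall slightly. All-cause tables are unchanged, so no severe event disappears from the report.

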8.4 Anti-drug Antibodies

1. Anti-ONO-4538 antibody

9. Planned Number of Subjects

Total of 93 subjects (41 subjects with squamous NSCLC and 52 subjects with non-squamous NSCLC)

10 Investigational Product Supply Restrictions

Each subject to whom the investigational product discontinuation criteria and individual subject discontinuation criteria are not applicable is eligible to receive the investigational product from the sponsor. The sponsor will stop supplying the investigational product if:

1. Ministry of Food and Drug Safety rejects the application for approval for the present indication.
2. The study is cancelled due to safety concerns.
3. The subject is able to receive the drugs through public or private health insurance.
4. An alternative therapy becomes available.

11. Planned Study Period

January 2014 to December 2021

The data cut-off may be performed based on progress of the clinical studies.

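### The time-to-toxicity endpoints censor event-free subjects at 28 days after the final dose, with no earlier stop when observation ends sooner through withdrawal, loss to follow-up or data cut-off

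*SAP*

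**What the plan says.** For time to a Grade 3 or higher adverse event, SAP 10.1.2 2)(1) states: "Data will be censored if the subject has no Grade 3 or higher adverse event at 28 days after the final dose", with one alternative: "or at the start of subsequent anti-cancer therapy for non-small-cell lung cancer after the final dose, whichever comes first". Item (2) carries the rule over: "Time to a Grade 3 or higher adverse drug reaction will be also calculated in the same manner". Item (3) repeats it for select adverse events: "Data will be censored if the subject has no select adverse event in any of the categories at 28 days after the final dose". Item (4) extends it to select adverse drug reactions.

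The results appear as plots under SAP 10.1.3 2)(11). That item asks for Kaplan-Meier curves of the select events and reactions, and adds: "Kaplan-Meier curves will also be displayed for time to onset of Grade 3 or higher adverse events and adverse drug reactions". It requests no median, landmark rate or interval.

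The documents foresee that observation may end before day 28:
- Protocol Table 4-3 has a visit for discontinuation within 28 days of the final dose, and it allows the 28-day visit up to 7 days early. Routine adverse event collection ends when the final tests are complete.
- Protocol section 11 says: "The data cut-off may be performed based on progress of the clinical studies".
- SAP 10.1.2 2)(5) counts deaths inside the window, as the "total number of subjects who have died during the period from the first dose of the study drug" up to the same end point.

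**The concern.** A Kaplan-Meier risk set should hold only subjects in whom an event could have been recorded. If a subject leaves 5 days after the last dose and is censored at day 28, 23 event-free days are credited that nobody observed. If a subject is still on treatment at a data cut and the last recorded dose is taken as the final dose, the censoring date falls after the data end. In both cases the denominator is too large and the plotted cumulative toxicity is too low.

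The SAP handles this differently for efficacy. In SAP 9.2.3, overall survival is censored at the last date known alive, progression-free survival and time to progression at the last evaluable imaging (or at treatment start if there is none), and duration of response at the last evaluable tumor assessment. Only the safety time-to-event rules use a date that can lie beyond the last observation. At stake are the shape of four sets of safety curves and whether two programmers would draw the same ones.

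**Working it through.** The plan gives no numerical figure for this analysis, so there is none to reproduce.

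**Unobserved time per subject.** Let g be the days from the last recorded dose to the end of observation. The overhang is 28 − g.
- Withdrawal 5 days after the last dose: 28 − 5 = 23 days.
- On treatment at a cut, dosed every 2 weeks on schedule: g is 0 to 14, so the overhang is 14 to 28 days. A permitted dosing delay makes g larger and the overhang smaller.
- The maximum is 28 days.

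**Effect on the curve.** The plotted quantity is 1 − Π(1 − d/n). The rule leaves the event counts d unchanged and enlarges n, so the curve can only fall relative to censoring at the last observed date.

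**Size.** None of these inputs is in the documents: cumulative incidence of 20% at 6 months with constant hazard; exponential time on drug with median 2.8 months (inside the 2.3 to 3.1 months that SAP section 1 gives for progression-free survival on docetaxel); 14-day dosing; uniform accrual over 12 months; a fraction lost at a uniform time in the 28 days after the final dose. I simulated 1,000,000 subjects per row, without deaths. Entries are 1 − KM in percent.

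| Scenario | 6 mo, as written | 6 mo, last observed | Gap | 12 mo, as written | 12 mo, last observed | Gap |
|---|---|---|---|---|---|---|
| Cut 2,000 days after last entry, no loss | 19.9 | 19.9 | 0.0 | 35.8 | 35.8 | 0.0 |
| Same, 10% lost | 19.7 | 19.9 | 0.2 | 35.7 | 36.0 | 0.3 |
| Same, 20% lost | 19.5 | 19.8 | 0.3 | 35.3 | 35.9 | 0.6 |
| Cut 180 days after last entry, no loss | 19.9 | 19.9 | 0.0 | 34.8 | 35.8 | 1.0 |
| Cut 30 days after last entry, no loss | 19.1 | 20.1 | 1.0 | 33.2 | 36.7 | 3.5 |
| Same, 10% lost | 18.8 | 19.9 | 1.1 | 32.2 | 35.8 | 3.6 |
| Same, 20% lost | 18.7 | 20.0 | 1.3 | 32.1 | 36.1 | 4.0 |

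With the 30-day cut and no loss, about 12 of 93 subjects are expected to be under observation at 6 months and fewer than one at 12 months. The 12-month gap therefore belongs to the far tail of the plot.

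**Sensitivity.**
- Accrual over 6 months with a 30-day cut and no loss: 17.2% against 20.0% at 6 months, with about 4 of 93 still at risk.
- Higher event rate (30% by week 12), long follow-up, 10% loss: 50.4% against 50.8% at day 168.
- The same rate with 6 months of accrual and a cut at 9 months: 49.0% against 50.9% at day 168, and 60.6% against 65.7% at day 252.

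**Deaths, taken separately.** With the table's assumptions, long follow-up and 20% dying without the event in the 28-day window, the 6-month figures are 19.6% as written, 19.9% with Kaplan-Meier censored at death, and 17.7% as cumulative incidence with death competing. In the higher-rate setting the day-252 figures are 64.4%, 65.4% and 55.4%. The written curve is below the first comparator and above the second.

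**The case against.** **The rule is silent rather than wrong.** It does not say that a subject who left on day 5 is assigned day 28, and a subject still on treatment has no final dose yet. A careful programmer would stop at the last observation. This stands, and it makes the point an omission to close. It does not remove the point, because day 28 is the only date written for a subject without the event or subsequent therapy.

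**A reader might infer that the curves are too low because dead subjects stay at risk.** The documents do not support that. The SAP grades adverse-event death as Grade 5, so such a death is itself an event for the Grade 3 or higher adverse event endpoint. For deaths that are not events, the direction depends on the comparator. A dead subject cannot have a later event, and against a competing-risk cumulative incidence the written curve is not too low.

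**The larger gaps need an early cut, and no cut-off date is given.** SAP 14.4 records 96 treated subjects by 27 February 2015, and SAP version 3.0 is dated 29 July 2021, which is 2,344 days later. An analysis under the current SAP is closest to the long-follow-up rows. A cut under version 2.0 (April 2015) is possible but undocumented. This stands.

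**Nothing inferential depends on it.** SAP 12.2 plans no tests, and SAP 10.1.3 only displays the curves. At 20% incidence the binomial standard error is √(0.2 × 0.8/93) = 4.1 points overall, and 5.5 (n = 52) to 6.2 (n = 41) points by histology. A gap of 0 to 0.5 point would not be visible. This also stands.

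**Conclusion.** The omission is real and minor. As written, items (1) to (4) of SAP 10.1.2 2) can keep withdrawn, lost or cut-off subjects at risk for up to 28 unobserved days, and for those subjects the effect on the curve is downward.

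The size is roughly 0 to 0.5 point at 6 months with long follow-up. With a cut soon after last entry it is about 1 to 1.4 points at 6 months, the upper end allowing for somewhat heavier loss than tabulated, and 3 to 4 points at 12 months. These ranges assume 20% incidence at 6 months and 12 months of accrual. A higher event rate or faster accrual combined with an early cut widens them.

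No downward bias is claimed for deaths; what is missing there is a statement of how death is handled. Adverse event incidence tables, death counts and the primary response rate do not use this rule and are unaffected.

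**What to change.** In SAP 10.1.2 2), define one censoring date for subjects without the event and apply it to all four endpoints: Grade 3 or higher adverse events, Grade 3 or higher adverse drug reactions, select adverse events and select adverse drug reactions. The date is the earliest of:
- 28 days after the final dose;
- start of subsequent NSCLC therapy;
- last adverse event assessment or withdrawal;
- data cut-off;
- death.

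Add a sentence saying whether death without the event is censored or treated as a competing event. If it is competing, SAP 10.1.3 2)(11) should name a cumulative incidence estimate in place of, or beside, the Kaplan-Meier curve. Also say that for subjects still on treatment at a cut, the cut-off date applies.

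The cost is a few SAP sentences and a small change to the derivation code. If the last adverse event assessment date is not already derived, it has to be added from the visit data. No new data collection is needed.
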